## **Introduction**

This Manual of Procedures (MOP) has been created to help build a framework upon which all research staff can base their approach to dealing with enrolling participants in the study and adhering to study protocol. The goal of this manual is to create more consistency across study researchers and students.

## **Brief Purpose of Study**

This study is designed to examine whether In Vivo nicotine replacement therapy (NRT) experience intervention will be effective in quitting smoking as compared to behavioral standard of care smoking cessation treatment. For this study, In Vivo experience is: the use of one of four different short-acting NRT products in conjunction with nicotine patches during session. Specialized counseling focused around the experience of NRT, including how the use of NRT may help with quitting smoking, side effects, and smoking cessation expectancies will also be utilized.

If eligible to participate, subjects will be randomized into one of the four Intervention (In-Vivo) groups or the control group. They will be asked to fill out forms regarding smoking behavior, demographics, medical information, and a contact sheet. Some questionnaires will be repeated at every visit and others will be repeated less frequently. Participants are asked to complete 13 weeks of intervention, comprised of five weeks of smoking cessation therapy (Intervention or Control; Weeks 1-5) and three treatment sessions designed to measure medication adherence (Weeks 6, 9 and 13). Following intervention completion, participants will be asked to return for a follow up visit at one month.

Participants in the Intervention groups will be asked to go as long as they can without smoking the day of the therapy sessions. They will put a nicotine patch on during each of the weekly sessions. During the first four weekly sessions, participants in the Intervention groups will also use a different form of short-acting NRT each week (nicotine gum, lozenge, inhaler, nasal spray) and in the fifth week, will select which short-acting medication they would prefer to use for the duration of the study. Participants will discuss the experience of wearing the patch and/or using the short-acting NRT while they are in session. The Control group will not use NRT medication during the sessions but will be given standard counseling regarding quitting smoking.

At each visit a carbon monoxide (CO) test will be administered (like an alcohol breathalyzer), which will show how much CO is in a participant's lungs as a result of smoking. A cotinine test will always be done at Baseline, and then at subsequent visits if the CO test indicates a participant is not smoking. Throughout the study, women of child bearing potential will be asked to give a urine sample to test for pregnancy a total of 4 times, and for all participants a urine drug screen will be completed at Baseline. See the chart below for more details regarding frequency of tests and questionnaires.

## Measurement Occurrence Chart

Data Collection Instrument	Baseline (1)	Wk1 (2)	Wk2 (3)	Wk3 (4)	Wk4 (5)	Wk5 (6)	Wk6 (7)	Wk9 (8)	Wk13 (9)	M1FU (10)
Screening Questionnaire (survey)										
Session Status (survey)										
Med Given (survey)		✓	✓	✓	✓	✓	✓	✓	✓	✓
CO Level	✓	✓	✓	✓	✓	✓	✓	✓	✓	✓
Cotinine Test	✓	✓	✓	✓	✓	✓	✓	✓	✓	✓
Pregnancy Test	✓				✓		✓	✓	✓	
Urine Drug Screen	✓									
Mini International Neuropsychiatric Interview Mini	✓									
Demographic Form (survey)	↓									
NRT Adherence (survey)		↓	↓	↓	↓	↓	↓	↓	↓	↓
Minnesota Nicotine Withdrawal Scale Pre (survey)	↓	↓	↓	↓	↓	↓	↓	↓	↓	↓
Questionnaire Of Smoking Urges Short Form Pre (survey)	↓	↓	↓	↓	↓	↓	↓	↓	↓	↓
Smoking History Form (survey)	↓									
Weekly Smoking Behavior	✓	✓	✓	✓	✓	✓	✓	✓	✓	✓
Thoughts About Abstinence (survey)	↓	↓	↓	↓	↓	↓	↓	↓	↓	↓
Fagerstrom Test For Nicotine Addiction (survey)	↓					↓	↓	↓	↓	↓
Perceived Stress Scale (survey)	↓	↓	↓	↓	↓	↓	↓	↓	↓	↓
Wisconsin Inventory of Smoking Dependence Motives (survey)	↓					↓	↓	↓	↓	↓
Treatment Expectations (survey)	↓	↓	↓	↓	↓	↓	↓	↓	↓	↓
Smoking Abstinence Questionnaire (survey)	↓					↓	↓	↓	↓	↓
Abstinence Related Motivational Engagement ARME (survey)	↓	↓	↓	↓	↓	↓	↓	↓	↓	↓
Attitudes About Nicotine Replacement Therapy (survey)	↓	↓	↓	↓	↓	↓	↓	↓	↓	↓
Treatment Satisfaction Survey (survey)						↓		↓	↓	↓
Credibility Expectancy Questionnaire CEQ (survey)						↓		↓	↓	↓
Symptom Side Effects (survey)	↓	↓	↓	↓	↓	↓	↓	↓	↓	
Barratt Impulsivity Scale	✓									
Pittsburgh Sleep Quality Index	✓	✓	✓	✓	✓	✓	✓	✓	✓	✓
Minnesota Nicotine Withdrawal Scale Post (survey)	↓	↓	↓	↓	↓	↓				
Questionnaire Of Smoking Urges Short Form Post (survey)	↓	↓	↓	↓	↓	↓				
Alliance Questionnaire						✓				
Alliance Questionnaire Therapist						✓				
Group Assignment (survey)										
Audio Recording Length		✓	✓	✓	✓	✓				

## Accessing the Shared Drive

1. Click on the home button at the bottom left hand corner of the computer screen.
2. Go to “Computer.”
3. Click on “PBN.” Enter your Blazer ID and password if necessary.
4. Click on “[name]-Lab.”
5. Click on the “NRT Sampling” folder (this is the folder for our study).

## Recruitment and Eligibility

### Subject Recruitment

Participants will be recruited from the community. Flyers describing the study will be placed in low income areas around the city. Potential participants should be instructed to call the study team for eligibility screening [contact].

### Subject Enrollment

#### Inclusion Criteria

- At least 18 years old
- Qualifying as low income (making <150% above the poverty line, or <\$22,260 as a single, or <\$45,570 for a family of four)
- Smoked at least 10 cigarettes per day (CPD) for the last year
- Live in an unrestricted environment (e.g., living in a halfway house, or independently)
- Expire carbon monoxide (CO) >8 ppm at Baseline
- Positive cotinine test at Baseline

#### Exclusion Criteria

- Pregnant or nursing
- Currently receiving treatment to quit smoking (enrolled in smoking cessation treatment program, using NRT products, or prescribed bupropion or varenicline)
- Known sensitivity to nicotine replacement or allergy to adhesive used in nicotine patches
- Trouble breathing, a pulmonary condition, or sinus problems
- Untreated severe angina or heart attack within last month
- TMJ (temporomandibular joint) problems (unable to use nicotine gum)
- Cognitive impairment or unstable psychiatric condition that interferes with the informed consent process
- Daily or exclusive use of other tobacco products (electronic cigarettes, little cigars, etc.)
- Non-English Speaking

#### Protocol for Enrollment

1. Check the Ineligible section of the Screening Form folder and/or Screening Database to see if the person inquiring has already been screened
2. Complete a Screening Form for each potential participant
3. If participant is ineligible, do not tell them they are ineligible until the screening form is complete
4. Enter the Screening Form into the Screening Database
5. File the Screening Form in the Screening Form folder according to eligibility. The folder is kept in the filing cabinet C in room L107B.

## Forms/Links

Screening Form → P:\[name]-Lab\NRT Sampling\Measures\Screening Form NRT R34  
Screening Database → Z:\[name]-Lab\NRT Sampling\Datasets\Screening

## Carbon Monoxide Monitor

### Carbon Monoxide Monitor Use Steps

1. Insert t-valve into the taper on the top of the machine case
2. Turn on machine
3. Put on gloves and attach a new white mini mouthpiece to the t-valve
4. Make sure machine is reading at zero
  - If it does not zero out, move black slider above the Vitalograph logo to left or right until it reads zero
5. Tell participant to take a deep breath, hold for 10 seconds, and breathe out slowly through the mouthpiece over a period of 20 seconds or more
6. Record the highest number from the machine on the NRT adherence sheet and enter into REDCap

\*\*You may also want to remind the participant of their CO level when you begin the therapy session with them. \*\*

### Carbon Monoxide Monitor and Intervention Sessions

- Participants are to provide a CO sample at each visit.
- **If they blow  $\leq 8$  on a Baseline visit, they are not eligible to participate**
- **If they blow  $\leq 3$  on subsequent visits, a cotinine test must be done and recorded in REDCap**

### Carbon Monoxide Gas Ordering

- CO gas is to be ordered through the Vitalograph website
- Email [name] to order: [[contact]](mailto:[contact])
- Link to website: <https://vitalograph.com/shop>

### Calibration Log

- T-valves must be replaced after every 50 uses (approximately every two months)

### Calibration

1. Turn on CO Breathalyzer Machine
2. Attach t-valve into the taper on the top of the machine case

3. Take CO calibration gas and insert end of gas tube into t-valve
4. Slowly open the gas cap (either twist open or push up) and watch the CO machine reader go up in number until it slows down. When the reader stays on the same number for approximately 5 seconds, you know it is now calibrated.
5. Close the gas tank by twisting the cap or pulling it down
6. Disconnect the gas tank
7. Leave the machine on until it brings the number back down to zero (approximately 30 seconds) then turn the machine off
8. Calibration is complete

## Carbon Monoxide Gas Disposal

- Throw in trash (safe gas) and make sure cap is opened all the way
- Each gas container has approximately enough pressure to calibrate a machine 5-6 times
- Need to replace when it runs low on pressure, or runs out of pressure (at 0 psi). You can read the pressure gauge to find out just how much pressure is in each canister.

Instructions: Return unused product to the supplier. If product must be disposed of on-site, incineration using a suitable flare is typically used. Disposal of carbon monoxide must be done in an environmentally acceptable manner in compliance with all applicable national and local codes. (Also known as: Throw in trash)

\*CO Machine Training Manual is located at: <https://vitalograph.co.uk/downloads/display/8>

## Urine Collection Protocol

- **WEAR GLOVES AT ALL TIMES WHEN HANDLING URINE SAMPLES.**
- Drug testing should be completed at Baseline appointment for all participants
- Cotinine testing is to be conducted Baseline appointment for all participants
- Cotinine testing is done at subsequent visits if the participant blows 3 or below on their CO test
  - Instructions for Cotinine tests located at: <http://www.xlar.com/I/NICOTINE-TEST.pdf>
- Pregnancy testing is completed at Baseline, Week 5 and Week 9
  - Instructions for Pregnancy tests are located at: <https://static.fishersci.com/cmsassets/downloads/segment/Healthcare/pdf/HCGdipPI23900527.pdf>
- We will conduct the pregnancy and cotinine testing for participants

## Collection

1. To prepare you will need:
  1. Urine cup
  2. Urine lid
  3. Cotinine test (for Baseline or when participant blows less than 3 on CO test)

4. Pregnancy test (for women at Baseline, Week 5 and Week 9)
5. Gloves
2. Urine cups and lids can be found in the filing cabinet in room L107E.
3. Escort participant to the bathroom
4. Test female urine for pregnancy
5. Test urine for cotinine at Baseline and if participant blows  $\leq 3$  on CO monitor at subsequent visits
6. Record drug and pregnancy test results in REDCap

## Surface Pros, REDCap, Dropbox, Digital Recorders

### Surface Pros

Surface Pros can be found in the locked desk drawers located in rooms L107A & B. At the beginning of each day, study staff will get both tablets out and turn them on to ensure they are fully charged and updated in preparation for the day's appointments.

***Login for Surface Pros and REDCap:*** Use your Blazer ID and password

***Wi-Fi Login:*** Be sure to use UABSecure network, which is secure (do NOT use UABStartHere or UABHS Public). You will only need to enter your credentials once. You will need to do this under your own login for each Surface Pro.

### ***Troubleshooting Wi-Fi Login:***

- Go to “Start” (flag at bottom left hand corner) and select Settings
- Select Network
- Disconnect from Wi-Fi and re-connect
- If that still does not work, reboot/shut-down surface pro and try again

### Entering New Participant Data:

1. Go the website <https://redcap.dom.uab.edu/redcap/index.php> and log into REDCap with your UAB BlazerID and password.
2. Click on **My Projects** in the upper left hand corner of the page.
3. From the **My Projects** page, select the Project Title **“NRT Sampling and Selection to Increase Medication Adherence”**
4. Click **Add/Edit Records** on the left side of the screen under the **Data Collection** tab and select **Arm 2: Pre-Randomization** from the drop down menu.
5. Click **Add New Record** to be taken to the **Record Home Page** of the new participant.
6. From this page select the Data Collection Instrument **CO Level** (Make sure to select the correct one, which is dependent upon which visit they have come in for) to begin the data collection process with the participant.

### Random Assignment:

Complete the Data Entry Process as instructed under **Entering New Participant**. One of the forms under the REDCap documents for the Baseline Visit (BL) is titled **Group Assignment**. Once in this form, click the randomize button on this document to randomly assign the participant.

### Adding to Existing Participant Data:

1. Go to the website <https://redcap.dom.uab.edu/redcap/index.php> and log into REDCap with your UAB BlazerID and password
2. Click on **My Projects** in the upper left hand corner of the page
3. From the **My Projects** page, select the Project Title **“NRT Sampling and Selection to Increase Medication Adherence”**
4. Click **Add/Edit Records** on the left side of the screen under the **Data Collection** tab
5. Select the existing participant’s ID # from the drop-down list that you would like to add the new data to
6. From the **Data Collection** page choose the desired data form under the correct study visit event to enter the data

### **Editing Data:**

1. Go the website <https://redcap.dom.uab.edu/redcap/index.php> and log into REDCap with your UAB BlazerID and password
2. Click on **My Projects** in the upper left hand corner of the page
3. From the **My Projects** page, select the Project Title **“NRT Sampling and Selection to Increase Medication Adherence”**
4. Click **Add/Edit Records** on the left side of the screen under the **Data Collection** tab
5. Select the existing participant’s ID # from the drop-down list that you would like to add the new data to

### **Survey Queue:**

The survey queue is a way for participants to fill out questionnaires in REDCap in a more user-friendly display. When in survey mode, the screen simply shows the questionnaire with a submit button at the bottom. Once begun, the questionnaires will automatically load in the appropriate order corresponding to whichever session or visit the participant is attending. If a subject accidentally forgets to answer something, the survey prevents them from moving on, which gives staff the opportunity to assist if necessary. It is very important to note that surveys must be completed in the order they are shown.

To access the survey queue:

- Follow the steps as above, titled “Entering New Participant Data” or “Adding to Existing Participant Data”, depending on whether you are working with a new or existing subject
- From the **Record Home Page**, select the **CO Level** Data Collection Instrument, corresponding to the appropriate appointment, e.g. Baseline, Week 1, etc.
- Toward the upper right corner of the form, there is a gray drop down box titled **“Survey Options.”** Click this box and select **“Open Survey.”** A new tab will open displaying the form now in survey display. If the tab does not open, try clicking **“Open Survey”** again or double-clicking.
- Staff should fill out **CO Level**, select **“Submit”**, and the next form will auto load. The survey queue is set up to stop before loading the questionnaires for participants. The screen will indicate you have finished with that set of surveys, and will provide a link at the bottom to start the next set to be filled out by the participant.

- When appropriate, select that link and have the participant proceed through the queue. The queue will automatically stop again before loading any other questionnaires intended to be filled out after the counseling session or completed by staff, for example.

\*\*You can access the survey queue from any of the measures set up as surveys by again selecting “**Open Survey**” from the gray “**Survey Queue**” drop down box toward the upper right corner of the page.

\*\*Surveys display on the **Record Home Page** as complete with a green circle and white check mark.

#### To edit data once surveys are complete:

- From the **Record Home Page** for a given subject, select the measure you want to edit
- In the red box toward the top of the form, select the gray button “**Edit Response**”
- Once desired changes have been made, select “**Save and Exit Form**” at the bottom

#### Audio Option in Questionnaires:

Within each questionnaire, click the dropdown box labeled “**Survey Options**”, then select “**Open Survey**.” This will open up the questionnaire in a new tab. On this new page, have the participant click on the speaker icon next to the question. The computer will read the question aloud. Once completed, click the submit button on the bottom of the page. Repeat the prior steps for the remainder of the necessary questionnaires.

#### Exporting to Excel/SPSS:

1. Go the website <https://redcap.dom.uab.edu/redcap/index.php> and log into REDCap with your UAB BlazerID and password
2. Click on **My Projects** in the upper left hand corner of the page
3. From the **My Projects** select the Project Title “**NRT Sampling and Selection to Increase Medication Adherence**”
4. Under the **Applications Tab** in the middle left hand column of the screen click on **Data Exports, Reports, and Stats**
5. To export all of the data from REDCap to SPSS click **Export Data** under the **View/Export Options** column for the row A.) All Data. Check the circle for the software you will be exporting the data to and then click **Export Data**
6. Download the 3 files to one folder, run the mapping file, then hit **Run All** (under run tab in the SPSS data module) after opening the SPSS folder. A new Untitled database will then be created. Name and save the database on the share drive.

#### Scheduling a New Participant:

1. Go the Google Calendar website <https://www.google.com/calendar> and log into the [name] Lab Google Calendar with the [name] Lab username and password
2. Check the **NRT Sampling Calendar** for availability.

3. Add the participant to the **NRT Sampling Calendar** by clicking on the designated day and time.
4. Fill out the **Title of Event** with either the participants' initials for a Baseline appointment or the participants' study ID, intervention type, session week, and who the session will be with.
5. Select the correct time and duration of the appointment.
6. Select save and make sure the appointment appears on the **NRT Sampling Calendar**.

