2. Administer the CO test. Refer to the CO directions under the "CO Monitor" section on **Page 8** of this manual. Record the CO level in REDCap.
  - If the CO level is 3 or below, you need to administer a urine cotinine test to confirm that the participant is using nicotine products.
3. Have the participant fill out all of the questionnaires related to the session in REDCap.
4. While the participant is filling out the questionnaires on REDCap, have REDCap open on the desktop and double check for participant entry errors as they progress through the questionnaires.
5. Ask the participant if they experienced any issues in the past week with the short-acting NRT they selected. If they report experiencing issues, follow the discussion guidelines in the therapist manual.
6. If the participant reports issues, determine whether the dosage of the short-acting NRT they selected should be lowered.
7. Remind the participant of the instructions on how to use the patches and gum/lozenges/inhaler/nasal spray and let them know they can reference their workbook if they forget.
8. Ask the participant if they have any questions.
9. Schedule the next appointment in three weeks (preferably the same day of the week and the same morning time). This appointment should be scheduled with another study staff member other than the therapist who saw the participant for the five weekly sessions.

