**Once you have it scheduled, make sure the appointment is placed in the [name] Lab Google Calendar.**

10. Give the participant 21 patches. The patches will last through to the next appointment.
11. Give the participant enough of the short-acting NRT they chose to last through to the next appointment.
12. Have the participant sign for the medication in the medication sign-out log.
13. Mark in the Medication Inventory Excel sheet how many of the patches and gum packages/lozenge quit tubes/inhaler cartridges/nasal spray bottles you have given out so that we maintain a running total of prescriptions we have on hand.
14. Compensate the participant on their Greenphire ClinCard.
15. Give the participant an appointment card. **Also, remind them to bring all used and unused patches, patch packets, and short-acting NRT back to the next appointment.**

### Week 9

1. Check to see if any information on participant's contact sheet needs to be updated.
2. Administer the CO test. Refer to the CO directions under the "CO Monitor" section on **Page 8** of this manual. Record the CO level in REDCap.
  - If the CO level is 3 or below, you need to administer a urine cotinine test to confirm that the participant is using nicotine products.
3. Have the participant fill out all of the questionnaires related to the session in REDCap.

4. While the participant is filling out the questionnaires on REDCap, have REDCap open on the desktop and double check for participant entry errors as they progress through the questionnaires.
5. Ask the participant if they experienced any issues in the past three weeks with the short-acting NRT they selected. If they report experiencing issues, follow the discussion guidelines in the therapist manual.
6. If the participant reports issues, determine whether the dosage of the short-acting NRT they selected should be lowered.
7. Remind the participant of the instructions on how to use the patches and gum/lozenges/inhaler/nasal spray and let them know they can reference their workbook if they forget.
8. Discuss the purpose of tapering medication dosage and review tapering instructions.
9. Ask the participant if they have any questions.
10. Schedule the next appointment in a month (preferably the same day of the week and the same morning time). This appointment should be scheduled with another study staff member other than the therapist who saw the participant for the five weekly sessions.

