NRT Adherence	X	X	X	X	X	X	X	X	X	

Note: BL=Baseline Assessment; S=session; WK=week; M=month; PS=Product Selection; ¹All participants will complete these surveys twice (at the beginning and end of session) during sessions 1-4.

Randomization. We anticipate enrolling 10 pre-pilot participants in 3 months and 80 participants in 20 months and, based on our previous study with this population, expect to retain at least 70% through the one month follow-up point. Randomization will occur after completion of the initial screening and assessment.

Primary Outcomes. Feasibility and acceptability will be measured through high study retention (70%) and recruitment (recruitment of all participants within 24 months) in our groups. Additional items of acceptability include high scores on treatment satisfaction and credibility/expectancies that are equal or higher to the SC

group. Medication adherence is a third primary outcome with expected differences between our groups. Adherence is notoriously difficult to determine. Self-reported adherence is not always reliable, particularly during treatment studies where there is a demand characteristic to report the desired targeted behavior⁷³⁻⁷⁴ (e.g., adherence to NRT). The behavioral methods described under the assessment section represent the best available self-report tools for determining NRT adherence (e.g., TLFB report, returning used NRT patches and used product blister packs/packaging). Adherence will be defined by self-report using the TLFB and verified through returned patches and packaging. Good adherence is defined by taking greater than 80% of doses of medication at each time point. We have used these techniques in previous studies with low income populations with good compliance for use of TLFB verified by return of NRT materials⁷⁵.

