Participant Tracking and Retention. Participants will attend four weekly intervention sessions and a Product Selection session at Week 5. They will receive a one week follow-up after starting medication as well as monthly follow-up at weeks 9 and 13 during the NRT administration. The final follow-up will occur one month post-intervention. For this study, we will follow our participants for one month after the end of NRT administration (~4 months total in the study). We will continue to use our standard methods for ensuring high retention including collecting contact information on the participant as well as obtaining the contact information of three close friends or family members and providing follow-up and reminder phone calls. We have used these methods with good success with our ongoing and previous projects with this population. Thus, we believe we can maintain high retention and follow-up throughout the study.

Data Management and Statistical Analysis. Data will be entered and stored on the UAB secured network. Data analyses will be performed by the PI who has a master's degree in biostatistics using SPSS.

To test Aim 1, the development and refinement of the In vivo intervention, we will pre-pilot the intervention with 10 participants. We will examine participant's responses on the Treatment Satisfaction Survey as well as examine other factors that participants mention to improve treatment. As the intervention is already developed, this phase will be primarily used to finalize study procedures and make modifications to the study protocol. We will not conduct any in depth interviews or use qualitative methods, but will rather use this as an opportunity to make minor adjustments to the protocol.

To Test Aim 2, feasibility and acceptability of the intervention, we will determine our rate of recruitment, retention and the credibility and expectancies for the intervention using descriptive statistics. We expect that the novel In vivo intervention will be both feasible and acceptable as evidenced by a high rate of recruitment and over 70% retention through follow-up, with no differences in attrition between the groups. In addition, we expect that In vivo intervention will be rated as high on treatment satisfaction, credibility, and expectancies for treatment relative to SC. We will use Chi-Square analyses to examine attrition and t-tests to examine treatment satisfaction scores, credibility, and expectancy differences between the groups.

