To test Aim 3, we will examine medication adherence during the 8 week intervention period between the intervention groups using Chi Square analyses at weeks 6, 9 and 13. Medication adherence will be defined as a self-reported use of taking 80% of medication as prescribed at each time point for both groups (adherent or not adherent). We can also look at adherence as a continuous proportion variable: adherence = number of doses taken / the number of doses given. We will also examine demographic and smoking characteristics (particularly withdrawal, cravings, abstinence self-efficacy, and NRT perceptions) that would be associated with medication adherence at weeks 6, 9 and 13 using logistic regression. These analyses will allow us to examine important associations with medication adherence in these groups.

To examine underlying factors believed to be important for medication adherence, particularly withdrawal, craving, self-efficacy, and perceptions of NRT, we will also examine these factors by intervention groups across time using paired t-tests, as appropriate. We are primarily interested in determining if our In vivo group had decreases in withdrawal and cravings, while increasing abstinence self-efficacy and NRT perceptions relative to the SC group. Given the pilot nature of this intervention, we will be able to examine 24-hour quit attempts and abstinence, but these factors are not the main focus on analyses as we will likely be underpowered to find significant differences on these outcomes with this small of a sample. While 80 participants may seem like a fairly large sample for a pilot study, a sample size between 500-600 participants is typical for most smoking cessation interventions and would be needed to examine important moderators and mediators of cessation. However, we will be able to obtain initial effect sizes that will be useful for determining the appropriate sample size for a fully-scaled R01 project in the future, if this intervention appears promising.

Missing data. There is a high likelihood that we will have participants who may miss an appointment, do not complete the study, or are otherwise lost to follow-up. Because of the potential of bias due to non-missing

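### The calendar title shows the arm at the visits where adherence is compared, and no step masks it when adherence is classified or analysed

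*Protocol*

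**What the plan says.** **Calendar.** Step 4 of the protocol section on scheduling a new participant sets the event title. A Baseline entry carries the participant's initials. Any other entry carries the "study ID, intervention type, session week, and who the session will be with". The calendar is opened with one shared lab username and password. No other title format appears in the manual.

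**Who takes the outcome visits.** At Week 5, in Groups A to D and in Control, staff are told of the Week 6 visit: "This appointment should be scheduled with another study staff member other than the therapist who saw the participant for the five weekly sessions". The Week 6, 9 and 13 steps repeat this for the Week 9, Week 13 and Month 1 visits. All of these go on the same lab calendar.

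**What is measured there.** The SAP names adherence as the third primary outcome. Under Aim 3: "Medication adherence will be defined as a self-reported use of taking 80% of medication as prescribed at each time point for both groups". The groups are compared "using Chi Square analyses at weeks 6, 9 and 13". The SAP's Primary Outcomes paragraph says the time-line follow-back report is to be verified by returned patches and packaging.

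**Analysis.** "Data analyses will be performed by the PI", using SPSS. The protocol's export instructions describe a full export of all data. The only reference to blinding in either document is to un-blinded adverse-event summaries for the DSMB.

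**The concern.** Adherence rests on what participants report, checked against what they bring back. When the two disagree, someone must decide which to believe, and neither document gives a rule for that decision. A person who knows the arm may, without intending it, question one group more closely or give the other the benefit of the doubt. The team developed the In vivo intervention and expects it to raise adherence, so an unmasked judgement would more plausibly lean that way.

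The arm label in the title serves no stated purpose at Weeks 6, 9 and 13. From Week 5 on, both groups follow the same visit steps and receive the patch with a chosen short-acting product. Disclosing the arm there adds an avoidable opening for bias in a primary outcome.

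**Working it through.** The plan gives no figure on this point, so the main check is to trace the text.

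1. *Does the title rule reach the outcome visits?* Step 4 sits under a heading about new participants, but its wording separates Baseline from every other visit. No later section exempts Weeks 6, 9 or 13. Yes.
2. *Are those visits on that calendar?* The Week 5 steps in all five groups, and the Week 6 and Week 9 steps, send the next appointment there. Yes.
3. *Are they the adherence time points?* Aim 3 uses Weeks 6, 9 and 13. Yes. Month 1 is also reassigned to other staff but is not an adherence comparison point.
4. *What part do staff play in the adherence data?* The evidence is mixed. The Measurement Occurrence Chart lists NRT Adherence as a survey, which participants complete themselves. At Weeks 6, 9 and 13 staff check entries as they are made. The Data Collection Parameters section has staff enter the tobacco and NRT calendars at each session visit, but no Week 6, 9 or 13 step repeats this. Participants are told to bring back used and unused product, yet those visits contain no step for counting it.
5. *Does any step hide the arm?* None was found for the visit, the classification, the export or the analysis.
6. *Is the title the only disclosure?* No. After randomization the REDCap questionnaires are those of the assigned group (Baseline Procedures). Workbooks differ by arm. The Week 6 and Week 9 steps refer staff to the therapist manual. Session recordings may be reviewed by any study member except the session's therapist. The SAP has the research assistants trained in both interventions.

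**Illustration only.** The documents give no rate of differential crediting. Assume true adherence of 30% in both arms, over-crediting of In vivo by 5 or 10 points, and n per arm of 40 (80 split equally) or 28 (0.70 × 40, the SAP's retention target). The chance of a significant two-sided test at one visit is approximately

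Φ((d − 1.96·s₀)/s₁) + Φ((−d − 1.96·s₀)/s₁),

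where d is the over-crediting, s₀ = √(2p̄(1−p̄)/n), p̄ is the mean of the two observed proportions, and s₁ = √(p₁(1−p₁)/n + p₂(1−p₂)/n).

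| n per arm | Observed 30% v 35% | Observed 30% v 40% |
|---|---|---|
| 28 | 6.8% | 12.1% |
| 40 | 7.6% | 15.4% |

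For example, with n = 40 and d = 0.10, s₀ = 0.1067 and s₁ = 0.1061, which gives 15.4%. At 40 per arm, 5 to 10 points is 2 to 4 people. The nominal rate is 5%. The table shows only how few reclassified people would matter. It does not estimate bias in this trial.

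**The case against.** The strongest objection is that no safeguard is being broken. A reader might infer that the manual sets up blinded assessors and then undoes this with a label. The documents do not support that. They give no reason for changing staff and never say that assessors are blinded. An equally natural aim is to spare participants from reporting missed doses to the person who counselled them, and that benefit survives if the new staff member knows the arm. This part of the objection stands.

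A reader might also take the SAP's caution about self-report, "particularly during treatment studies where there is a demand characteristic to report the desired targeted behavior", as an admission of assessor bias. It describes pressure on the participant, who knows which treatment was given. A calendar title does not change that.

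Three further inferences go beyond the text: that visit staff record adherence themselves, that they count returns at Weeks 6, 9 and 13, and that the investigator personally does the adherent/not-adherent coding. The 80% threshold, and the formula of doses taken over doses given, also limit discretion. In addition, daily phone surveys from Week 5 to Week 13 ask about patch and short-acting NRT use with no assessor present. The SAP does not name them as the source of the primary outcome, but they offer a cross-check.

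Finally, removing the label alone would not mask the visit, for the reasons in step 6 of the working. That stands too. It does not touch the classification step, which can be masked whatever the visit staff knew.

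**Conclusion.** The point holds as a cheap improvement. It is not a contradiction in the plan or a breach of a stated blinding rule. The text establishes three things: the arm is in the title of every non-Baseline visit, the adherence visits are among them and are taken by staff other than the therapist, and nothing masks the arm at assessment, classification or analysis.

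The size of any bias cannot be computed from the documents. The illustrative 6.8% to 15.4% rests wholly on an assumed 30% base rate, an assumed 5 to 10 points of over-crediting, and equal arms.

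The more important exposure is the unmasked reconciliation of self-report with returned product, for which no rule is given. The calendar title is the lesser and more visible part.

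**What to change.** 1. From Week 6 on, title calendar entries with study ID, visit week and staff member only. Treat this as a partial measure.
2. Write down how a disagreement between the time-line follow-back and the returns is settled. Then classify each participant as adherent or not at Weeks 6, 9 and 13 on an export without the group field and without event names or forms that identify the group. Leave out the Week 1 to 4 medication records, because Control receives no medication then. Express the Week 5 patch supply as the total of 7 in every group, because Intervention participants leave with 6 plus one worn and Control participants with 7. Freeze the variable, then merge the arm.
3. State in the report that staff at the outcome visits were not fully masked.

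The cost is one manual edit and one extra export step, with no added staff or visits. Masking at the visit stays imperfect, since REDCap forms, workbooks, the therapist manual and participants themselves can reveal the arm. If the visits are already complete, item 1 no longer applies. Item 2 is still possible if adherence has not yet been classified with the arm in view, and item 3 applies either way.
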